at 4 months, a 1-sided alpha level of 0.025, at least 85% power and under the assumption that the true difference in the means is 0.3 requires 262 participants (131 per arm). This number has been increased to allow up to 10% loss to follow-up or iron supplementation for those initially not requiring supplements (such individuals will be excluded from the primary analysis: see Section 12 for further details), thus the sample size is 292. For efficiency, participants will be enrolled into both parts of the quantitative study.

For efficiency, participants will be enrolled into both parts of the quantitative study.

Sample size justification

Cross-sectional study: Since all potential donors will contribute to the estimate of the proportion of potential donors who are deferred due to low haemoglobin, the estimate of this proportion will be sufficiently accurate to allow for comparisons against yearly rates. As stated above, the annual proportion of deferrals from 2015-2018 ranged from 33-53%. If we assume that 5 blood donors attempt to donate each business day, then there should be about 600 donation attempts over the 6-month enrolment period. Table 1 shows values for the prevalence of low haemoglobin, the corresponding margin of error and the corresponding 95% confidence interval. For example, if the prevalence of low haemoglobin leading to deferral is 50% then a 95% confidence interval would be (46%, 53%) which allows for determination of the prevalence in a range that is smaller than the range of yearly estimates. Note: these estimates were obtained using the usual normal approximation to the sampling distribution of a proportion without a continuity correction.

Table 1: Precision of prevalence estimates for low haemoglobin leading to deferral.

| Prevalence | Margin of error | 95% confidence interval |
|-------------------|------------------------|--------------------------------|
| 0.2 | 0.032 | 0.17, 0.23 |

| | | |
|-----|-------|------------|
| 0.3 | 0.037 | 0.26, 0.34 |
| 0.4 | 0.039 | 0.36, 0.44 |
| 0.5 | 0.040 | 0.46, 0.54 |
| 0.6 | 0.039 | 0.56, 0.64 |

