Parallel groups study: The primary outcome for this portion of the study is haemoglobin levels at 4 months. Formally the null hypothesis for this outcome is inferiority of treatment of low haemoglobin with iron supplementation among those with low haemoglobin at baseline to no treatment among those without low haemoglobin at baseline. The non-inferiority margin is fixed at a value of 1.0 g/dL. Based on recent work in west Africa, the DCC has access to haemoglobin measurements from 1548 individuals between the ages of 17 and 60 who weigh at least 50 kg. Among these individuals the standard deviation of haemoglobin was 1.89 g/dL (the mean was 13.4 g/dL). These individuals did not pass the strict screening criteria used by the NBSG, so this estimate might be slightly inflated and so our power calculations may be somewhat conservative. We specify an alpha level of 0.025 and require power of at least 85%. With these values we can determine the number of participants per arm if we assume a value for the true difference between the groups (the absolute value of this difference must be less than our margin and will generally be negative when the margin is positive to be consistent with the lack of superiority of iron supplementation). Table 3 presents the number of participants per arm under these assumptions for a selection of values for the true difference. We assume that the true difference is -0.3 g/dL and obtain a sample size of 131 participants per arm. If the true difference is larger than -0.3 g/dL (e.g., if there is no difference) then the power will exceed 85%. To allow for loss to follow-up and some participants requiring iron supplementation due to incident ID or IDA the sample size has been increased to 292.

Table 3: Number of participants per arm for 1-sided alpha of 0.025 and power of at least 85%.

| Mean Hb treated-mean Hb control (i.e., true treatment difference) | Sample size (per group) |
|---|-------------------------|
| 0 | 65 |
| -0.1 | 80 |
| -0.2 | 101 |
| -0.3 | 131 |
| -0.4 | 179 |

Study site and Population

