The use of simple, clear, detailed written and verbal instructions regarding therapy, possible side effects of iron supplementation and tests required for the study increases comprehension of the purpose and importance of the study and yields better adherence to the trial. Study research assistants are to regularly communicate with donors in the study and provide feedback to them using a structured guideline. Reminders will be sent to donors for their study visits by the research assistants. A consumer-friendly brochure on safe use of medicines including food interactions and medicine interactions involving iron is to be provided to participants.

The key to the success of retention and follow-up will be attention to detail, consistency of the research team and trust among the potential blood donors and staff. The staff will contact potential blood donors immediately and reschedule appointments when missed. Close monitoring of participants' visits and need for return appointments with follow-up telephone calls are key elements for monitoring attendance and prevention of study participants' being lost to follow-up.

Every attempt will be made by the study team to contact participants prior to their scheduled visit based on the allotted schedule for participants on both arms of the study. Identification of a stable contact person (such as a neighbor or a friend) who does not live with the study participant's family, but always knows his or her

whereabouts will assist in tracking study participants and will decrease the number lost to follow up.

Safety Assessment

Definitions

- *Adverse Event (AE)*

An AE is any untoward or unfavourable medical occurrence in a study participant, including any abnormal sign (e.g., abnormal physical exam or laboratory finding), symptom, or disease, temporally associated with their participation in research. Only AEs potentially related to iron supplementation will be recorded as AEs.

At each follow-up visit all participants will be asked if they have experienced each item from a list of common side effects of iron supplementation. Furthermore, the occurrence of additional AEs will be sought by non-directive questioning of the study participant at each visit during the study. AEs also may be detected when they are volunteered by the study participants during or between visits or through physical examination findings, laboratory test findings, or other assessments.

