However, it is anticipated that AEs will occur infrequently in this population. There is no predefined type or frequency of AEs or SAEs for a stopping rule in this study. Review of SAEs and deaths on study will be performed routinely by the DSMB. If a safety concern arises that warrants review for possible study termination, the DSMB (or party identifying such concern) will notify the NHLBI immediately. Enrolment in the study may be temporarily halted for further review of safety data. This further assessment of safety data will include review by the DSMB, which may include a recommendation to terminate the study early. Termination of the clinical study may also occur due to a regulatory authority decision or if the sponsor or regulatory authority decides that subject safety may be compromised by continuing in the study. If the study is halted temporarily or prematurely terminated, a written statement fully documenting the reasons for study halt or termination will be provided to the Institutional Review Board (IRB)/ Independent Ethics Committee (IEC) and NHLBI.

Covid-19 Mitigation Strategies

Staff contact with participants for follow-up biweekly by phone for adherence and feedback. During study visits staff and participants will practice social distancing when possible and wear face masks that cover the mouth and nose. The study will provide facilities for frequent hand washing and alcohol-based sanitizers.

Halting Enrolment for Safety Reasons

The study may be discontinued at any time by the IRB, OSMD/DSMB or NHLBI as part of their duties to ensure that research participants are protected.

Data Analysis

- ***Qualitative Data Analysis***

Qualitative data collection and analysis will proceed simultaneously. In all, ten focus groups of 8-10 participants purposively selected with one group from each blood donation group categories (i) religious organizations, (ii) educational institutions, (iii) corporate institutions, (iv) organized community groups, and (v) walk-in blood donors. The aim of the focus groups is to identify barriers and recommendations for using iron supplementation and nutritional counseling to increase the blood donor pool. These will be gender-sensitive such that each focus group is equally split by gender (e.g., 4-5 females, 4-5 males). The female and male focus groups will meet in separate spaces so only one gender will be present. Thus, there is one male and one female group for each donation category.

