Several secondary outcomes relate to the safety of iron supplementation. To maximize the power to detect an association between group membership and safety outcomes a composite of SAEs, gastro-intestinal problems, malaria, and bacterial infections will be constructed and compared between the groups. The frequency of this composite will be compared between groups using Fisher's exact test. Furthermore, logistic regression models will be fit with group membership, sex, and age as covariates and the odds ratio associated with group membership will be estimated along with a 95% confidence interval. Components of the composite will also be investigated using a similar approach. The incidence of grade 3 or 4 AEs will be treated in a similar fashion. The frequency of responses to specific questions about known side effects to iron supplementation will be compared between the groups using logistic regression, controlling for sex and age. Each question will be investigated in addition to a response to any of the questions.

Since the treatment is not assigned at random there is a strong potential that confounders will introduce bias into the estimates of the treatment effects. As an attempt to remedy this, sensitivity analyses using inverse probability weighting will be conducted. If we use to represent group membership for participant i and Z_i is a vector of predictors for this participant, the first step of the analysis is to estimate the stabilized inverse probability of "treatment" weights W_i for subject i , $W_i = P(X_i = x_i)/P(X_i = x_i|Z_i)$. An estimate of $P(X_i = x_i|Z_i)$ can be obtained by logistic regression and $P(X_i = x_i)$ can be estimated by the sample proportion. One then uses these weights in a regression model to adjust for participant characteristics that differ between the groups.

The incidence of ID or IDA will be examined among participants in the control group (who are not ID and do not have IDA at baseline by definition). These estimates will be in the form of events per unit time. If someone is found to be ID or IDA and then resolves that person re-enters the risk pool for an event. To account for multiple events in the same individual, the generalized estimating equation version of Poisson regression will be used with the robust standard error if necessary. The same approach will be used to examine the incidence of ID and IDA separately.

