### Secondary analyses of secondary outcomes related to safety and feasibility

To maximize the power to detect an association between group membership and safety outcomes, a composite of grade 3 and 4 AEs, SAEs, gastro-intestinal problems, malaria, and bacterial infections will be constructed and compared between the groups.

The frequency of this composite will be compared between groups using Fisher's exact test. Furthermore, logistic regression models will be fit with group membership, sex, and age as covariates and the odds ratio associated with group membership will be estimated along with a 95% confidence interval. These models will be parameterized so that an OR greater than 1 indicates that the intervention group has a higher incidence of negative outcomes. Components of the composite will also be investigated using a similar approach.

The questions about known side effects to iron supplementation ask: Has the participant experienced any of the following since the last visit (mark all that apply)?

- Unpleasant taste.
- Constipation.
- Dark tools.
- Nausea.
- Vomiting.
- Abdominal pain.
- Diarrhea.
- Other; specify.

The incidence of each of these outcomes over follow-up will be computed and logistic regression models will examine the impact of group membership, sex, and age on these outcomes. The odds ratio and a 95% confidence interval for the group membership variable will be used to summarize the association. Models which look at the incidence of any of these outcomes will also be examined and an odds ratio and 95% confidence interval will be used to summarize the relationship.

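### The individual side-effect items are compared by ordinary logistic regression alone, with no rule for an item that no control reports, where the odds ratio is infinite

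*Protocol*

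**What the plan says.** The Protocol (Data Analysis, Quantitative Data Analysis) gives safety outcomes two different treatments.

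- **Composite, components and grade 3-4 events.** The composite of serious events, gastrointestinal problems, malaria and bacterial infections is compared by Fisher's exact test. Logistic regression on group, sex and age then gives an odds ratio and 95% interval. Components are to be handled in a like manner, and so are grade 3 or 4 events. SAP 7.2.2 puts grade 3 and 4 events inside the composite and again has components follow the composite.
- **Side-effect checklist.** Here "responses to specific questions about known side effects to iron supplementation will be compared between the groups using logistic regression", adjusted for sex and age. Each item is modelled, as is a report of any item. The SAP lists the items and says: "The odds ratio and a 95% confidence interval for the group membership variable will be used to summarize the association". No exact test is assigned. The SAP also has the incidence of each item computed.

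Neither document says what to do when an arm has no events, or whether intervals and tests are Wald, likelihood-based or exact.

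On expected frequency, the Protocol's safety section says "it is anticipated that AEs will occur infrequently in this population" and "Only AEs potentially related to iron supplementation will be recorded as AEs". The checklist is put to participants in both groups at every follow-up visit. Controls take no iron at enrolment but receive it if they become anaemic or iron deficient (SAP 4). They stay in the control group, which is defined at enrolment (SAP 7.2).

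**The concern.** The checklist items are known effects of iron, and one arm starts without iron. An item reported only by people on iron is therefore a foreseeable result, and it would be a clear signal. Ordinary logistic regression has no finite estimate for that table. For these items it is also the only planned comparison, and its odds ratio and interval are the planned summary.

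The safety profile of iron, judged against the untreated group, is part of acceptability under the primary objective. If the planned summary fails, a substitute must be chosen after the counts are known, in a study that is not blinded (SAP 2.3).

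**Working it through.** **Group sizes.** The documents give no event rate or power for safety, so the only figure to reproduce is the sample size. Inputs from the Protocol (Sample Size): "a 1-sided alpha level of 0.025, at least 85% power and under the assumption that the true difference in the means is 0.3"; "The non-inferiority margin is fixed at a value of 1.0 g/dL"; "the standard deviation of haemoglobin was 1.89 g/dL".

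n per arm = 2 × (1.960 + 1.036)² × 1.89² / (1.0 − 0.3)² = 64.1 / 0.49 = 130.9, so 131. Total 262; 262 / 0.90 = 291.1, so 292. Both match the plan. Equal groups give 146 per arm.

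**Chance that no control reports an item.** P(0 of 146) = (1 − p)^146. The control rate p is an assumption, so a range is shown.

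| Assumed control rate | P(0 of 146) |
|---|---|
| 0.2% | 0.75 |
| 0.5% | 0.48 |
| 1% | 0.23 |
| 2% | 0.05 |
| 5% | 0.0006 |

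These figures ignore controls who start iron during follow-up, which lowers the chance of an empty cell.

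**What the planned model returns.** Logistic regression of event on group, sex and age, 146 per arm, with simulated sex and age and illustrative counts (iron v control):

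| Counts | ML log OR (SE) | Wald p | Likelihood-ratio p | Fisher p | Firth OR (95% profile CI) | Firth p |
|---|---|---|---|---|---|---|
| 5 v 0 | 17.8 (3,259) | 0.996 | 0.009 | 0.060 | 10.8 (1.2 to 1,427) | 0.03 |
| 6 v 0 | 19.1 (5,228) | 0.997 | 0.003 | 0.030 | 14.5 (1.7 to 1,902) | 0.010 |
| 10 v 0 | 18.6 (3,287) | 0.995 | 0.0002 | 0.0017 | 21.9 (2.8 to 2,823) | 0.0008 |
| 20 v 0 | 18.4 (2,009) | 0.993 | 5e-8 | 9e-7 | 48 (6.5 to 6,145) | 3e-7 |
| 20 v 1 | 3.16 (1.0) | 0.002 | 2e-6 | 1e-5 | 15.9 (4.0 to 145) | 4e-6 |
| 20 v 3 | 2.05 (0.6) | 0.001 | 9e-5 | 3e-4 | 6.7 (2.4 to 25.9) | 1e-4 |

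With an empty control cell, the log odds ratio of 18 to 19 is only where the iterations stopped; the true maximum is at infinity. At 20 v 0 the Wald interval on the log scale is 18.4 ± 1.96 × 2,009, about −3,920 to 3,957, which is zero to infinity as an odds ratio. Results at 131 per arm are the same in kind.

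Two further points follow from the table. A single control event restores a finite estimate and a usable Wald test. With an empty cell and few events, the valid alternatives can disagree: at 5 v 0 the likelihood-ratio and Firth p-values fall below 0.05 and Fisher's does not. That is a reason to name the method in advance.

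**The case against.** Much of the case on the other side stands.

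- **Serious and grade 3-4 events.** A reader might infer that these too would be reported with a p-value near 1. The documents do not support that. Fisher's exact test is planned for the composite and is carried over to the components (which include serious events) and to grade 3 or 4 events. Its p-value is valid with an empty cell. Only the adjusted odds ratio and interval can fail there.
- **Wald is not named.** A p-value near 1 is a Wald result. The likelihood-ratio test from the same model gives 0.003 at 6 v 0. For these items the SAP specifies an odds ratio and interval, not a p-value, and computes incidence as well, so a lopsided split would be visible. This removes any claim that a harm would necessarily be reported as non-significant. It does not rescue the planned odds ratio, which is infinite whichever test is used.
- **An empty control cell may not occur.** The statements that adverse events will be infrequent and that only iron-related ones are recorded concern adverse-event recording. The checklist is solicited from everyone, and nausea, constipation, diarrhoea and abdominal pain also occur without iron. Some controls will start iron: if 14 of 146 did so and each had a 30% chance of reporting an item (illustrative), the chance that none would is 0.7^14 = 0.7%; with 7 it is 8%. These points make an empty cell unlikely for common symptoms, but not for rarer items.
- **Loss of power.** A reader might turn the empty-cell probabilities into detection rates of 52% or 77%. Those are simply 1 − 0.48 and 1 − 0.23, with the Wald test assumed as well. They add no evidence.

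**Conclusion.** The point holds for the individual side-effect items and the any-item response. Logistic regression is their only planned comparison, and it has no finite odds ratio when an arm has no events. How often this would happen is unknown: the chance per item runs from 48% at an assumed control rate of 0.5% to 0.06% at 5%, before allowing for controls who start iron. Unpleasant taste and dark stools are plausible candidates; the any-item response and common gastrointestinal symptoms are not. The loss of the odds ratio and its upper limit is certain once the cell is empty. The loss of the whole interval and of the p-value depends on Wald methods being used, which the plan leaves open.

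For serious events, composite components and grade 3-4 events the exposure is limited to the adjusted odds ratio and its interval. This is a modest gap in secondary analyses of a pilot, worth closing because the safety comparison serves the primary objective.

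**What to change.** In SAP 7.2.2, and in the safety paragraph of the Protocol's Quantitative Data Analysis section:

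1. Add Fisher's exact test for each side-effect item and for any item.
2. State outright that Fisher's exact test applies to serious events, to each composite component and to grade 3-4 events, rather than leaving this to a cross-reference.
3. Fit the adjusted safety models by Firth penalised logistic regression with profile penalised-likelihood 95% intervals, at least whenever either arm has zero or very few events. If it is not used throughout, give the count that triggers it.
4. Report the risk difference with its 95% interval alongside.

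The cost is a few sentences and a model option available in SAS and R, both already named in the SAP. No extra data or participants are needed, and the SAP can be updated until database lock. The downside is shrinkage of the odds ratio: from 7.8 to 6.7 at 20 v 3 and from 23.7 to 15.9 at 20 v 1, and less where events are common. Upper limits stay very wide when a cell is empty, so the risk difference will often be the more readable summary.

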APPENDIX 1 –Data Collection Instruments

FOCUS GROUP DISCUSSION GUIDE

Aim: *To identify barriers and recommendations for using iron supplementation and nutritional counseling to increase the blood donor pool.*

DATE: _____ **LOCATION:** _____

NUMBER OF FGD PARTICIPANTS: _____

FGD FACILITATOR: _____

FGD NOTE-TAKER: _____

FGD START TIME (HH:MM): _____

FGD END TIME (HH:MM): _____

Welcome the focus group participants:

Good morning/afternoon. My name is _____ and I will be your moderator for this focus group discussion. I am part of the BLOODSAFE Project Team, which is a group of researchers from within and outside of Ghana carrying out a study to understand and improve blood donation in Ghana.

I am a trained focus group moderator and I would like to hear your honest opinions about the topics we will discuss today. There is no right or wrong answer to the questions I'm going to ask. Please just relax and enjoy the discussion.

Please keep in mind that your participation is completely voluntary. If for any reason you wish to leave the discussion, you may do so.

I am accompanied by _____ who will be responsible for note taking. Other project staff from the Project Team will also be in the room observing the focus group discussion. Kindly state whether it is okay to continue with the discussion.

Rules or Guidelines

- You have been invited here to offer your views and opinions. We will like to have a successful discussion where everyone feels comfortable expressing their perspectives and opinions
- Again, there are no right or wrong answers and it is okay to be critical. I want to hear your views and opinions about whether you like or dislike something you see or hear.
- There will be observers.
- You may excuse yourself from the conversation at any time for any reason.

- This session will be audio taped so that we can capture everything being discussed today, for the purpose of listening to it again to get the message well. All the discussions will remain confidential. Please feel free to say exactly what is on your mind as nothing will be attributed to any particular person in our report.
- Everyone's participation is important.
- Please speak one at a time and avoid side conversations.
- Please use any of your names that you are comfortable with only during the discussion.
- Respect each other's opinions.
- Lastly, please turn off the ringers on your cell phones.

Views from Individual Members in the FGD

Demography and social characteristics of participants

- Name: _____
- Name of Community (Group): _____
- Age: _____
- Sex: _____
- Highest Educational level attained: _____
- Religion: _____
- Ethnic background: _____
- Occupation: _____

You participated in this project, which involved blood donors.

- How did the project influence your knowledge about iron supplementation for deferred blood donors?

Probe:

- *Are you aware of any cultural reasons why people do not use iron supplements?*
- *Are you aware of any religious reasons why people do not use iron supplements?*
- *Did it increase your awareness of iron supplements?*
- *Did it improve your knowledge on the usefulness of iron supplements?*
- *Do you believe people will like to use iron supplements after the project?*

- How did the project influence your attitudes to iron supplementation for deferred blood donors?

Probe:

- *Are you aware of any cultural reasons why people do not use iron supplements?*
- *Are you aware of any religious reasons why people do not use iron supplements?*
- *Did it increase your attitude to use of iron supplements?*
- *Do you believe people will like to use iron supplements after the project?*

- How did the project influence your beliefs about iron supplementation for deferred blood donors?

Probe:

- *Are you aware of any cultural beliefs why people do not use iron supplements?*
- *Are you aware of any religious beliefs why people do not use iron supplements?*
- *Did it influence your beliefs (either positively or negatively) of iron supplements?*
- *Do you believe people will like to use iron supplements after the project?*

- What influenced your participation in this project?

Probe:

- *Was the colour of the iron supplement culturally acceptable?*
- *Was the dosage of the iron supplement culturally acceptable?*
- *Did taking these supplement affect your participation, negatively or positively?*
- *Was there in any religious and cultural aspects of your life that affected how you participated in the project generally?*

- Please describe the counselling you received about iron supplementation?

Probe:

- *Were you given adequate information and guidance on eating iron or micronutrient-rich foods?*
- *Were any cultural or religious concerns or inhibitions to eating these foods addressed?*

- *Were there issues you did not understand during the counselling sessions?*
- *Were there issues you disagreed with during the counselling sessions?*
- *What other information would have preferred to receive?*

- How will you describe the quality of the nutritional counselling you received as part of the project?

Probe:

- *Were you given adequate information and guidance on nutrition?*
- *Were any cultural or religious concerns or inhibitions on adequate nutrition addressed?*
- *Were there issues you did not understand during the counselling sessions?*
- *Were there issues you disagreed with during the counselling sessions?*
- *What other information would have preferred to receive?*

- From your experience, what do you consider as barriers to people like you participating in an iron supplementation and nutritional counselling project?

Probe:

- *Do you have any concerns or fears in being able to adhere to the use of the iron supplements/ medications?*
- *Do you have any concerns or fears on the side effects of the medications?*
- *Do you have any concerns in making time for the counselling sessions and visits?*
- *Do you have any concerns or fears of repeat donation if your iron stores improve?*
- *Do you have any concerns or fears that iron supplements may cause you to eat more?*
- *Do you have any concerns or fears that iron supplements may cause you to eat more and come with additional cost to you?*

- How do you think we could carry out this intervention differently to ensure people participate fully?

Probe:

What do you propose to be solutions to these?

- *Concerns or fears in being able to adhere to the use of the iron supplements/ medications?*
- *Concerns or fears on the side effects of the medications?*
- *Concerns in making time for the counselling sessions and visits?*
- *Concerns or fears of repeat donation if your iron stores improve?*
- *Concerns or fears that iron supplements may cause you to eat more?*
- *Concerns or fears that iron supplements may cause you to eat more and come with additional cost to you?*

• What recommendations do you have for using iron supplementation and nutritional counselling for improving the blood donor pool?

Probe:

- *Do you have any ideas from the discussions so far on the use of iron supplementation and nutritional counselling for improving the blood donor pool in Ghana?*

Composite Views from Members in the FGD

- How many participants have ever donated blood? _____

- How many times have participants been donating blood?
average: _____ minimum: _____
maximum: _____
- How long ago was the last donation?
average: _____ minimum: _____
maximum: _____
- How many participants have ever used iron supplementation after blood donation?

- How many participants have ever had nutritional counselling after blood donation?

- What are the views of participants on the usefulness of iron supplementation and nutritional counselling after blood donation?

- What are the key suggestions / recommendation to improve blood donation in the community/group?

- What will make participants be willing to re-donate blood?

- Any other comments you have on the project?

KEY INFORMANT INTERVIEW GUIDE

Basic characteristics

- Name: _____
- Age: _____
- Sex: _____

- Designation/position _____
- Organization: _____
- How do you envisage iron supplementation to influence knowledge of deferred blood donors?

Probe:

- *Are you aware of any cultural reasons why people do not use iron supplements?*
- *Are you aware of any religious reasons why people do not use iron supplements?*
- *Do you believe people will like to use iron supplements after the project?*
- How do you envisage iron supplementation to influence attitudes of deferred blood donors?

Probe:

- *Are you aware of any cultural attitudes why people do not use iron supplements?*
- *Are you aware of any religious attitudes why people do not use iron supplements?*
- *Do you believe people will like to use iron supplements after the project?*
- How do you envisage iron supplementation to influence belief systems of deferred blood donors?

Probe:

- *Are you aware of any cultural beliefs why people do not use iron supplements?*
- *Are you aware of any religious beliefs why people do not use iron supplements?*
- *Do you believe people will like to use iron supplements after the project?*
- What aspects of your culture affected your participation in the project?

Probe:

- *Will the colour of the iron supplement affect culturally acceptability?*
- *Will the dosage (number of tablets or frequency of dosing in a day) of the iron supplement affect culturally acceptability?*

- *Are there in any religious and cultural aspects that may influence the use of iron supplementation by deferred donors?*
- What should go into the quality and quantity of the counseling on taking iron as recommended for deferred blood donors?

Probe:

- *What key issues should be discussed?*
- *What other information would you prefer to include?*

- From your experience, what do you consider as barriers to deferred donors participating in an iron supplementation and nutritional counseling project?

Probe:

- *What are the fears and concerns?*
- What do you consider as solutions to the barriers?

Probe:

What do you propose to be solutions to these?

- *Concerns or fears in being able to adhere to the use of the iron supplements/ medications*
- *Concerns or fears on the side effects of the medications*
- *Concerns in making time for the counseling sessions and visits?*
- *Do you have any concerns or fears of repeat donation if iron stores improve?*
- What recommendations do you have for using iron supplementation and nutritional counseling for improving the blood donor pool?

Probe:

- *Do you have any ideas from the discussions so far on the use of iron supplementation and nutritional counseling for improving the blood donor pool in Ghana?*
- Any policy guide or direction on use of iron supplementation for deferred blood donors?

National Blood Service Ghana Donor Clinical Record

NBSG/DS/DC/F-001
Ver6
July 2020

Date _____

Venue _____

